3.5.3 Exploratory Analyses

The exploratory analyses will be conducted using the PPS and FAS.

The change of the weekly average of at-home BP from Baseline to each schedule post-Baseline visit, and the change and percent change from Baseline to each schedule post-Baseline visit in angiotensin II, renin (Plasma renin activity [PRA]; active renin mass concentration [ARC]), and plasma aldosterone will be compared between ISIS 757456 80 mg group and placebo group. The data will be analyzed in a similar way to the primary analysis. For the at-home BP analysis, subsequent SBP and DBP measurements will be completely removed from this exploratory analysis once the subjects received first administration of antihypertensive therapy during the study.

The percentage of subjects reaching the following goals for the in-clinic BP over time will be summarized, comparison of which will be made between ISIS 757456 80-mg group and placebo group using Fisher's exact test. Subsequent SBP and DBP measurements will be completely removed from this exploratory analysis once the subjects received first administration of antihypertensive therapy during the study.

- Percentage of subjects reaching SBP goal of ≤ 140 mmHg
- Percentage of subjects reaching DBP goal of ≤ 90 mmHg
- Percentage of subjects reaching both goals of SBP ≤ 140 mmHg and DBP ≤ 90 mmHg

The antihypertensive therapy will be identified through medical review when database is locked. The percentage of subjects requiring antihypertensive therapy during the study will be compared between ISIS 757456 80 mg group and placebo group in PPS and FAS using Chi-Square test or Fisher's exact test as appropriate. The time in days from first dose of Study Drug to the first administration of antihypertensive therapy during the study will be summarized using the following descriptive statistics: mean, standard deviation, median, P25, P75, and minimum and maximum. The Kaplan-Meier curves [1] for time to the first administration of antihypertensive therapy will be provided for ISIS 757456 80 mg group and placebo group, comparison of which may be made statistically using the log rank test. The time to the first administration of antihypertensive therapy will be calculated as:

- [Date of the first administration of antihypertensive therapy – Date of first dose of study drug +1]

Patients who did not receive any antihypertensive therapy during the study will be censored at the date of end of study.

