5.1. Inclusion Criteria

1. Must have given written informed consent (signed and dated) and any authorizations required by local law and be able to comply with all study requirements
2. Males or females aged 18-72 inclusive and weighing $\geq 50 \text{ kg}$ at the time of informed consent

3. Satisfy the following:
 - a. Females: must be non-pregnant and non-lactating, and either:
 - i. surgically sterile (e.g., tubal occlusion, hysterectomy, bilateral salpingectomy, bilateral oophorectomy) or,
 - ii. post-menopausal (defined as 12 months of spontaneous amenorrhea in females > 55 years of age or, in females ≤ 55 years, 12 months of spontaneous amenorrhea without an alternative medical cause and follicle stimulating hormone (FSH) levels in the postmenopausal range for the laboratory involved)
 - b. Males: Surgically sterile (i.e., bilateral orchidectomy) or abstinent*, if engaged in sexual relations with a woman of child-bearing potential (WOCBP), the subject or subject's non-pregnant female partner must be using a highly effective contraceptive method (refer to Section 6.3.1) from the time of signing the informed consent form until at least 13 weeks after the last dose of Study Drug (ISIS 757456 or placebo)

* True abstinence (i.e., refraining from heterosexual intercourse throughout the duration of study participation) is only acceptable. Periodic abstinence (e.g., calendar, ovulation, symptothermal, post-ovulation methods), declaration of abstinence for the duration of a trial and withdrawal are not acceptable methods of contraception
4. Willing to refrain from strenuous exercise/activity (e.g., heavy lifting, weight training, intense aerobics classes, etc.) for at least 24 hrs prior to study visits
5. BMI ≤ 35.0 kg/m²
6. Brachial circumference is ≥ 22 and ≤ 37 cm (8.7 and 14.6 inches)
7. Subject must have been diagnosed with essential hypertension for a minimum of 3 months prior to screening
8. At Screening, the subject must have a plasma AGT concentration ≥ 20 µg/mL
9. At Screening, the subject must have been on a stable regimen of antihypertensive medications (a total of 2) for at least 1 month prior to screening, using either an angiotensin-converting enzyme inhibitor (ACEi) or an angiotensin II receptor blocker (ARB), as well as a single other antihypertensive medication in the following categories:
 - a. beta blocker
 - i. acebutolol (≤ 400 mg q.d.)
 - ii. atenolol (≤ 50 mg q.d.)
 - iii. betaxolol (≤ 10 mg q.d.)
 - iv. bisoprolol (≤ 5 mg q.d.)

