2. Prior to Study Day 64 in the Post-Treatment Period or in the Washout Period, should a subject's BPM exceed 170 mmHg (systolic) or 110 mmHg (diastolic) a second measurement must be done within a 30-minute period. If the subject's BP is $>$ 170 mmHg (systolic) or $>$ 110 mmHg (diastolic) within the 30-minute period, an additional BP measurement should be taken within 48 hours at the Study Center, regardless of whether the initial BP measurements were taken in clinic or at home. If the subject then experiences an additional BP measurement $>$ 170 mmHg (systolic) or $>$ 110 mmHg (diastolic) (confirmed by triplicate measurement at the Study Center), they will then be withdrawn from further blinded, randomized treatment. The subject's pre-study antihypertensive medication(s) may be added back per Investigator and Sponsor Medical Monitor judgement. The subject will continue to be followed per protocol in the study. Follow-up for subjects that screen fail due to blood pressure inclusion criteria (see Section 5.1) will not be necessary.
3. On or after Study Day 64 in the Post-Treatment Period, should a subject's BPM exceed 140 mmHg (systolic) or 90 mmHg (diastolic) a second measurement must be done within a 30-minute period. If the subject's BP is $>$ 140 mmHg (systolic) or $>$ 90 mmHg (diastolic) within the 30-minute period, an additional BP measurement should be taken within 48 hours at the Study Center, regardless of whether the initial BP measurements were taken in clinic or at home. If the subject then experiences an additional BP measurement $>$ 140 mmHg (systolic) or $>$ 90 mmHg (diastolic) (confirmed by triplicate measurement at the Study Center), the subject's pre-study antihypertensive medication(s) may be added back per Investigator and Sponsor Medical Monitor judgement. The subject will continue to be followed per protocol in the study.

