1.1 Study Overview

This will be a Phase 2, double-blind, randomized, placebo-controlled study of ISIS 757456 conducted in mild hypertensive subjects on an ACEi/ARB and an additional hypertensive medication. Subjects will be stratified based on a screening plasma AGT concentration ($\leq 30 \mu\text{g/mL}$ vs. $> 30 \mu\text{g/mL}$) and randomized in a 2:1 ratio to receive a once-weekly subcutaneous (SC) treatment and an additional loading dose on Study Day 3 with either ISIS 757456 80 mg or placebo for 6 weeks.

[figure not shown]
All subjects will complete a 13-week Post-Treatment Period. In the Post-Treatment Period, should a subject's sitting BP on home monitoring exceed 140 mmHg systolic or 100 mmHg diastolic on 2 consecutive days (confirmed by triplicate measurement at the Study Center), the subject's initial hypertension (HTN) medication(s) may be added back per Investigator and Sponsor Medical Monitor judgment and the subject will continue to be followed per protocol in the study.

[REDACTED] All Study Drug injections will be SC administered in the clinic.

This study will be conducted at multiple centers in the United States. Approximately 30 subjects are planned to be enrolled in this study.

The study will consist of screen, run-in, washout (WO), treatment, and post-treatment. The overall length of a subject's participation will be approximately 25 weeks (up to 3 weeks for screening, 1-week run-in, 2 weeks for WO, a 6-week Treatment Period, and 13 weeks of Post-Treatment Evaluation Period).

The study design and treatment schema are depicted as follows:

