3 ANALYSIS PLAN

3.1 General Overview of Analyses

Descriptive summary statistics including number of subjects, mean, median, standard deviation, standard error of mean, 25th percentile, 75th percentile, minimum, and maximum for continuous variables, and counts and percentages for categorical variables will be used to summarize most data. All statistical tests will be conducted using 2-sided tests with 5% Type I error rate unless otherwise stated.

[figure not shown]
PK parameters will be summarized using include number of subjects, mean, standard deviation, coefficient of variation (CV), geometric mean, median, minimum, and maximum.

Baseline definition:

The baseline for plasma AGT will be define as the average of all values on or after Study Day -7 and prior to the first dose of Study Drug. The baseline for all other assessments will be defined as the last non-missing measurement prior to the first dose, unless otherwise specified.

Analytical visits:

Data will be summarized using the visit labels provided in the data. Multiple results with the same visit label will be averaged. Results with visit labels as "Unscheduled" will not be included in the by-visit summary tables and figures except for determining baseline and the analysis of confirmed ALT/AST category (see section 3.7.3) but will be presented in data listings.

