3.3 Statistical Methods

3.3.1 Subject Populations Analyzed

The following analysis populations are defined for this study:

- Full Analysis Set (FAS): All randomized subjects who have received at least 1 injection of Study Drug (ISIS 757456 or Placebo) and who have at least 1 post-Baseline efficacy or exploratory measurements.
- Per Protocol Set (PPS): All FAS subjects who received at least 5 of the 7 doses of Study Drug, did not receive antihypertensive medications during the Treatment Period and prior to Study Day 43, and have no significant protocol deviations that would be expected to affect efficacy or exploratory assessments.

- Safety Set: All subjects who are randomized and receive at least 1 dose of Study Drug.
- PK Set: All subjects who are randomized and receive at least 1 dose of ISIS 757456 and have at least 1 evaluable PK sample.

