3.5.2 Secondary Efficacy Analyses

The secondary efficacy analyses will be performed in a similar way to the primary analysis, which include:

- Comparison of change and percent change from Baseline to each schedule post-Baseline visit in AGT between ISIS 757456 80 mg group and placebo group in PPS and FAS
- Comparison of change from Baseline to each schedule post-Baseline visit in in-clinic SBP and DBP between ISIS 757456 80 mg group and placebo group in PPS and FAS. Subsequent SBP and DBP measurements will be completely removed from this analysis once the subjects received first administration of antihypertensive therapy during the study.

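### After antihypertensives restart, the SAP drops BP readings but by default keeps angiotensin II, renin and aldosterone values, so the late exploratory biomarker comparisons mix drug effect with rescue

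*Combined protocol and SAP*

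**What the plan says.** - **BP.** For in-clinic BP, SAP 3.5.2 states: "Subsequent SBP and DBP measurements will be completely removed from this analysis once the subjects received first administration of antihypertensive therapy during the study". SAP 3.5.3 repeats the rule for BP goals and, separately, for home readings: "For the at-home BP analysis, subsequent SBP and DBP measurements will be completely removed from this exploratory analysis once the subjects received first administration" (again, of an antihypertensive).
- **Biomarkers.** Angiotensin II, PRA, ARC and aldosterone share a paragraph with at-home BP in SAP 3.5.3 and are compared in PPS and FAS by the primary method. That method (SAP 3.5.1) has no restart rule. SAP 3.3.2 says only that missing values are not imputed.
- **PPS.** It requires that subjects "did not receive antihypertensive medications during the Treatment Period and prior to Study Day 43" (SAP 3.3.1). Later use does not exclude anyone.
- **Pre-study regimen.** Protocol 5.1, criterion 9, requires two drugs (the first is described as "using either an angiotensin-converting enzyme inhibitor (ACEi) or an angiotensin II receptor blocker (ARB"), with one further agent from another class. Protocol 2.5.1 lists ACEi and ARB among compounds blocking components of the pathway that the study drug targets.
- **Add-back.** Protocol 8.5.3 lets pre-study medication be resumed, at the judgement of the investigator and the sponsor's medical monitor. The trigger falls to a confirmed reading above 140 systolic or 90 diastolic "On or after Study Day 64 in the Post-Treatment Period".

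**The concern.** Within one paragraph the SAP treats restart as contaminating BP but says nothing about markers of the system on which part of the restarted regimen acts. The biomarker baseline is the last pre-dose value, taken after washout. For a subject who restarts an ACEi or ARB, the later change from baseline includes the move from off to on that drug.

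Restart is triggered by BP, which the study drug is expected to lower, so restart could differ between arms. The SAP itself plans to compare restart percentages and time to restart by arm. At stake is whether a late difference in these four markers can be read as the study drug's own effect on the system.

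**Working it through.** **1. Post-restart handling, side by side**

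| Outcome | Section | Values after first antihypertensive |
|---|---|---|
| In-clinic SBP, DBP | SAP 3.5.2 | Removed |
| At-home BP | SAP 3.5.3 | Removed |
| BP goals | SAP 3.5.3 | Removed |
| Angiotensin II, PRA, ARC, aldosterone | SAP 3.5.3, method of 3.5.1 | No rule; kept by default |

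**2. Visits exposed**

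The Exploratory row of protocol Appendix A gives post-dose samples on Days 22, 43, 64, 78, 106 and 127.

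- Days 78, 106 and 127 follow the switch to the 140/90 trigger. Entry required off-drug SBP above 140 (criterion 11), so restart is foreseeable.
- Day 64 mostly precedes a restart under that trigger, which needs a repeat within 30 minutes and a further Study Center reading within 48 hours.
- Day 64 and earlier can be affected through other triggers: above 170/110 (protocol 8.5.3 item 2 and 8.6.5 item 2), or the 140/100 wording of protocol 3.1 and SAP 1.1. In the PPS, Day 22 is protected, and Day 43 is protected against earlier restart.

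**3. Illustrative size**

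The documents state no figure to reproduce. Inputs from the SAP:

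- "Approximately 30 subjects are planned to be enrolled in this study" (SAP 1.1).
- Subjects are "randomized in a 2:1 ratio to receive a once-weekly subcutaneous (SC) treatment" (SAP 1.1), so 30 × 2/3 = 20 active and 30 × 1/3 = 10 placebo.
- "All statistical tests will be conducted using 2-sided tests with 5% Type I error rate unless otherwise stated" (SAP 3.1).

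Restart shares and the marker shift on restart are assumed.

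Spurious difference (absolute) = (restart share, placebo − restart share, active) × shift in SD. With a 1 SD shift:

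- 10-point gap: 0.10 × 1 = 0.1 SD
- 50-point gap: 0.50 × 1 = 0.5 SD
- no gap: 0 × 1 = 0

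The rejection rate with no drug effect was simulated: two-sample t-test, 20 against 10, two-sided 0.05, 20,000 runs, stratum ignored. Each cell gives shifts of 0.5 / 1 / 1.5 SD.

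| Restart, placebo/active | Spurious difference (SD) | Rejection rate (%) |
|---|---|---|
| 40%/40% | 0 / 0 / 0 | 5.0 / 5.0 / 5.0 |
| 30%/10% | 0.10 / 0.20 / 0.30 | 6.0 / 8.2 / 10.9 |
| 50%/30% | 0.10 / 0.20 / 0.30 | 5.6 / 7.4 / 9.9 |
| 70%/40% | 0.15 / 0.30 / 0.45 | 6.4 / 10.4 / 15.1 |
| 80%/30% | 0.25 / 0.50 / 0.75 | 9.3 / 21.2 / 35.3 |

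This treats every restart as shifting the marker. The documents do not give the sign of the shift for any marker, so no direction is claimed.

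**4. What removal would cost**

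Power for an assumed 1 SD difference, normal approximation: Φ(1/√(1/n_placebo + 1/n_active) − 1.96).

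- All values, 10 and 20: Φ(2.58 − 1.96) = 73%
- 40%/40%, leaving 6 and 12: 52%
- 30%/10%, leaving 7 and 18: 61%
- 50%/30%, leaving 5 and 14: 48%
- 70%/40%, leaving 3 and 12: 34%
- 80%/30%, leaving 2 and 14: 26%

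**The case against.** **The restarted drug need not be the ACEi or ARB.** Add-back is optional and may cover only one of the two drugs. This stands. A reader might infer that any post-rescue difference merely shows who restarted an ACEi or ARB. The documents do not support that: only restarters' values can shift, and the arm difference mixes drug effect with rescue.

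**Four of the six visits seem exposed.** A reader might count Day 64 because the threshold changes that day. Under that trigger, apart from visit-window edge cases, the Day 64 sample comes before any restart, so three visits are clearly exposed.

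**Keeping all values is legitimate.** It is a valid randomized comparison of drug plus rescue. That stands, but the SAP does not say that this is the intended quantity, and for BP it does the opposite.

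**Removal has its own bias.** Those who remain are subjects whose BP stayed controlled, which is a post-randomization outcome, and few placebo values are left. This stands, and it rules out simply making the BP rule the main biomarker analysis.

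**Rescue will be visible anyway.** SAP 3.5.3 plans restart percentages and Kaplan-Meier curves by arm, and SAP 3.7.6 summarizes concomitant medication by ATC class and arm. A reader could judge whether restart differed, but none of this separates rescue from drug effect in the biomarker comparison.

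**Conclusion.** The gap is real, although post-restart biomarkers are kept by silence and not by a stated choice. The late exploratory comparisons of the four markers estimate drug plus rescue. They are biased for the drug's own effect if restart of drugs acting on the pathway differs by arm.

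The size cannot be determined from the documents. The 0.1 to 0.5 SD range is illustrative: it rests on an assumed 10 to 50 point difference in restart and an assumed 1 SD shift, and it is zero with equal restart.

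A reader might infer that the trial's evidence on mechanism is compromised. It is not. The drug's target is plasma AGT, and the primary Day 43 AGT analysis in the PPS is unaffected, as that set excludes earlier antihypertensive use. What is affected is late, off-treatment, exploratory follow-up.

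**What to change.** In SAP 3.5.3:

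1. Report angiotensin II, PRA, ARC and aldosterone at each visit in two ways: with all values, labelled as drug plus rescue, and with values after the first antihypertensive removed, matching the BP rule.
2. Tabulate by arm and visit the number of subjects who have restarted and whether an ACEi or ARB was included.
3. State that the removal version is selective toward subjects whose BP stayed controlled and has few late placebo values, so neither version should be read alone.

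The cost is one or two extra tables. Restart dates are already derived for the Kaplan-Meier analysis, and reinstated drugs are recorded as concomitant medication, so no new data are needed.

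The restart triggers in protocol 3.1 and SAP 1.1 differ from those in protocol 8.5.3. These passages must be reconciled, because they determine when post-restart values begin.

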6.1.4. Treatment Period

Eligible subjects will be administered Study Drug (ISIS 757456 or placebo) on a weekly basis (6 weeks) as well as an additional dose on Study Day 3 for a total of 7 doses. Review of the at-home blood pressures and the in-clinic BP should be performed prior to administering the Study Drug.

Safety and clinical laboratory evaluations as well as blood sampling for PK analysis will be performed periodically throughout the Treatment Period ([Appendix A](#), [Appendix B](#), and [Appendix C](#)). Any AEs and concomitant medications will be recorded. If antihypertensive medications are re-instated this will be captured in the concomitant medications eCRF. All safety data including AEs, at home and in-clinic BP, and concomitant medications will be reviewed by the Sponsor's Medical Monitor or designee on an ongoing basis throughout the trial.

Subjects will continue at home BP and HR monitoring during the Treatment Period as outlined in Section [6.1.1.3](#) and [Appendix A](#). Subjects who discontinue the Treatment Period early will continue in the study following the post-treatment evaluations (Section [6.1.5](#))

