10.6.5. Exploratory Analyses

The change of the weekly average of at-home BP from Baseline to each schedule post-Baseline visit, and the change and percent change from Baseline to each schedule post-Baseline visit in angiotensin II, renin (Plasma renin activity [PRA]; active renin mass concentration [ARC]), and plasma aldosterone will be compared between ISIS 757456 80 mg group and placebo group in PPS and FAS. The data will be analyzed in a similar way to the primary analysis.

The percentage of subjects reaching the following goals for the in-clinic BP over time will be summarized, comparison of which will be made between ISIS 757456 80-mg group and placebo group using Fisher's exact test.

- Percentage of subjects reaching SBP goal of ≤ 140 mmHg
- Percentage of subjects reaching DBP goal of ≤ 90 mmHg
- Percentage of subjects reaching both goals of SBP ≤ 140 mmHg and DBP ≤ 90 mmHg

In addition, the percentage of subjects requiring antihypertensive therapy during the study, as well as the time in days from first dose of Study Drug to the first administration of antihypertensive therapy during the study will be compared between ISIS 757456 80-mg group and placebo group in PPS and FAS. The analyses will be detailed in the SAP.

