3.3.2 Handling of Missing Data

Missing values will not be imputed.

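### SAP 3.5.3 removes blood pressure after restarted antihypertensives without stating the goal-rate denominator, so above-goal subjects can drop out of the Day 78, 106 and 127 combined-goal tests

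*Combined protocol and SAP*

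**What the plan says.** SAP 3.5.3 compares, by Fisher's exact test in the PPS and FAS, the percentage of subjects with in-clinic SBP ≤ 140, DBP ≤ 90, and both. It states that "subsequent SBP and DBP measurements will be completely removed from this exploratory analysis once the subjects received first administration of antihypertensive therapy"; the sentence appears for at-home pressure and again for the in-clinic goals. Use is established at the end: "The antihypertensive therapy will be identified through medical review when database is locked". SAP 3.3.2 adds "Missing values will not be imputed". No denominator is given for the goal percentages.

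Protocol 10.6.5 describes the same analysis ("The percentage of subjects reaching the following goals for the in-clinic BP over time will be summarized, comparison of which will be made") without a removal rule.

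Protocol 8.5.3 item 3 sets the trigger from Study Day 64. It starts when a subject's "BPM exceed 140 mmHg (systolic) or 90 mmHg (diastolic) a second measurement must be done within a 30-minute period", and further confirmation at the Study Center is required. The pre-study drugs then "may be added back per Investigator and Sponsor Medical Monitor judgement". Item 3 also says: "The subject will continue to be followed per protocol in the study". Scheduled visits after Day 64 are Days 78, 106 and 127 (protocol 3.4.4). Protocol 6.1.4 says of restarts: "If antihypertensive medications are re-instated this will be captured in the concomitant medications eCRF".

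SAP 3.3.1 excludes a subject from the PPS for antihypertensive use in the Treatment Period and before Day 43. A subject first treated from Day 64 is not excluded from either set on that ground.

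**The concern.** The add-back trigger (above 140 or above 90) is the complement of the combined goal (≤ 140 and ≤ 90). If removal also takes the subject out of the denominator, subjects leave the test because they failed the goal. Those who remain are selected for success, and both arms look better than they are. Placebo has about 10 subjects and more of them above goal, so it is depleted faster.

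The match is exact only for the combined goal. A subject treated for diastolic pressure alone may still meet the systolic goal, and the reverse. The trigger may also start from a home reading, while the goal uses clinic readings.

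**Working it through.** **No figure to reproduce.** The documents give no goal rate, rescue rate or standard deviation for this analysis. Everything below is illustrative. From the documents: about 30 subjects randomized 2:1, so 20 v 10; two-sided 5% tests; the goals, trigger and visits above.

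**Step 1: which readings are open.** Either removed subjects leave the denominator (available case, which fits removal plus no imputation), or the denominator is the whole FAS or PPS and a removed subject is not at goal.

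**Step 2: fixed example.** Assume untreated pressure is at the combined goal in 10/20 active and 2/10 placebo, and half of those above goal are treated: 10 × 0.5 = 5 active and 8 × 0.5 = 4 placebo.
- Available case: 10/(20 − 5) = 10/15 = 67% v 2/(10 − 4) = 2/6 = 33%; Fisher p = 0.33.
- Fixed denominator: 10/20 = 50% v 2/10 = 20%; p = 0.24.
- Limit, all above-goal subjects treated, available case: 10/10 v 2/2, so 100% in both arms and p = 1.00.

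With true rate g and a fraction r of above-goal subjects treated, the available-case rate is g / [g + (1 − g)(1 − r)].
- Equal r = 0.5: 0.5/0.75 = 67% and 0.2/0.6 = 33%. The difference is 33 points against a true 30. Exact Fisher power falls from 0.27 with no rescue to 0.20.
- r = 0.4 active, 0.8 placebo: 0.5/0.80 = 62% and 0.2/0.36 = 56%. The difference is 7 points.
- No effect (g = 0.3 in both arms), r = 0.3 active, 0.8 placebo: 0.3/0.79 = 38% and 0.3/0.44 = 68%. The test rejects about 12% of the time.

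**Step 3: simulation over visits.** Assumed: untreated SBP mean 148, between-subject SD 9, visit SD 8; DBP mean 88, SDs 7 and 5; SBP-DBP correlation 0.5; effect −10/−5 mmHg; entry on Day -7 SBP above 140 and up to 165. The trigger applies at each visit from Day 64 when two readings are each above 140 or above 90. Add-back follows with probability 25, 50 or 90% **per trigger**, and later values are removed. Available-case rates average trials with at least one untreated subject in the arm. Figures carry Monte Carlo error of a point or two.

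| Combined goal | 25% | 50% | 90% |
|---|---|---|---|
| Placebo left of 10, Day 78 | 8.1 | 6.2 | 3.1 |
| Placebo left of 10, Day 106 | 6.6 | 4.0 | 1.5 |
| Placebo left of 10, Day 127 | 5.5 | 2.8 | 0.9 |
| Available case, placebo Day 78 (true 14%) | 16% | 18% | 26% |
| Available case, placebo Day 127 (true 15%) | 19% | 27% | 45% |
| Available case, active Day 127 (true 45%) | 52% | 58% | 67% |
| Treated = not at goal, placebo Day 127 | 10% | 7% | 4% |
| Treated = not at goal, active Day 127 | 39% | 34% | 28% |
| Fisher power Day 127, available case | 13% | 4% | 1% |
| Fisher power Day 127, treated = not at goal | 26% | 20% | 13% |

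The probabilities act repeatedly, so placebo subjects treated by Day 127 are (10 − 5.5)/10 = 45%, (10 − 2.8)/10 = 72% and (10 − 0.9)/10 = 91%. Power with no removal is about 30%.

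Day 127 arm difference, true 45 − 15 = 30 points:
- Available case: 52 − 19 = 33, 58 − 27 = 31, 67 − 45 = 22.
- Treated as not at goal: 39 − 10 = 29, 34 − 7 = 27, 28 − 4 = 24.

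With other means and SDs (DBP mean 84 or 92, SBP mean 152, SBP SDs 7/6 or 11/10), the placebo Day 127 available-case rate is 14–22/19–29/40–47% against a true 10–17%. Home-reading triggers were not modelled, so removal may be understated for a given add-back probability.

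**The case against.** **The not-at-goal rule is biased too.** This stands. It understates off-therapy goal rates in both arms by about as much as the available case overstates them at 25 and 50% per trigger, and it depends on discretionary prescribing. For the DBP-only goal it is far off in the model: placebo Day 127 33/18/7% against a true 56%.

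**The plan already shows much of this.** Largely right. SAP 3.1 plans numbers of subjects, counts and percentages. SAP 3.5.3 compares the proportion needing antihypertensives and plots time to first use. SAP 3.7 and 3.7.4 summarize blood pressure by visit in the Safety Set with no removal rule, though without a test. None of these settles the goal-rate denominator.

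**Removing pressure on restarted drugs is legitimate in a washout design.** Agreed. The gap is the denominator, not the wish to describe off-therapy pressure.

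**Stronger readings that a reader might infer:**
- Protocol 10.6.5 has no removal rule, so pressure on restarted drugs might seem countable. It is not: the SAP's explicit rule governs, because SAP section 1 makes the SAP the guide for the analysis.
- Every above-goal subject might seem to leave, giving 100% in both arms. Add-back is discretionary, so that is only the limiting case.
- A bias for or against the drug might seem to follow. With equal add-back at 25 or 50% per trigger the difference barely moves; with unequal add-back it can shrink, reverse or appear from nothing. The documents do not say which pattern would occur.

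**Conclusion.** The concern holds for the combined goal at Days 78, 106 and 127, on the available-case reading. Under the whole-set denominator, the only other reading, it does not arise. The main harms are inflated rates in both arms and lost precision. In the model the inflation is small at Day 78 (placebo 16/18/26% against 14%) and largest at Day 127. Its size rests on an unknown rescue rate and on assumed means, SDs and effect. If the effect halves by Day 127, power is at most 4% under any rule and the power gain disappears.

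Severity is minor. The endpoint is exploratory and three late visits carry the problem. Nine of the 12 post-baseline visits fall on or before Day 64 and are largely unaffected under protocol 8.5.3; only subjects treated earlier under the 170/110 rules are lost from them. The primary Day 43 AGT analysis is untouched. SAP 3.5.2 applies the same removal to SBP and DBP change, which lowers n at the late visits, but the direction of any bias in that mean difference is not determined. A reader should not infer that the secondary SBP analysis is invalid.

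**What to change.** 1. **SAP 3.5.3, combined goal.** Use all subjects in the analysis set (FAS, and PPS) as denominator and count visits after first antihypertensive use as goal not met. State how visits missed for other reasons count. Show the available-case rate with its n alongside. Describe the result as a composite that depends on discretionary prescribing and understates off-therapy goal rates in both arms. For the SBP-only and DBP-only goals, show both rates without letting the composite lead.
2. **SAP 3.5.2, optional.** Add a between-arm sensitivity analysis of SBP and DBP change that keeps values collected after rescue. Numbers per visit and a descriptive Safety Set summary are already planned.
3. **Separately**, reconcile the Post-Treatment add-back criteria. Protocol 3.1 and SAP 1.1 give 140/100 on 2 consecutive home-monitoring days with no Day 64 limit, whereas protocol 8.5.3 gives 140/90 from Day 64 and 170/110 before it. These affect how many subjects are treated and when. No view is taken on which is right.

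Items 1 and 2 cost SAP wording and a few table columns. No new data are needed, because restarts are recorded and treated subjects stay in follow-up. The price of item 1 is the understatement shown above; what it buys is a fixed denominator and precision.
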